3.3.3 Rationale for Collection of Survival Data in Cohort C

Patients with IPF have a very poor prognosis despite the availability of pirfenidone and nintedanib. Median survival remains low, between 2–5 years (Jo et al. 2018). IPF is the primary cause of death for 60% of patients with IPF, with death commonly occurring after an acute exacerbation of the disease. When an acute exacerbation of IPF is not the cause of death, other common causes include acute coronary syndromes, congestive heart failure, lung cancer, infection, and venous thromboembolic disease (Frankel and Schwarz 2009).

For patients who are unable or unwilling to continue with study treatment and/or assessments, the Sponsor will continue to collect their survival data unless patients withdraw consent to do so.

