4. MATERIALS AND METHODS

4.1 PATIENTS

4.1.1 Inclusion Criteria

Approximately 600–700 patients with IPF will be enrolled in this study.

Patients must meet the following criteria for study entry:

- Signed Informed Consent Form
- In the opinion of the Principle Investigator, participation in the study is in the best interest of the patient

- Ability to comply with the requirements of the study protocol, according to the investigator's best judgment
- Taken part in a previous study of PRM-151, as follows:
 - Participated in Study PRM-151-202 (completed the 28-week placebo-controlled period and entered the OLE), and tolerated the study drug in the opinion of the investigator (Cohort A) OR
 - Completed study treatment in Study WA42293 (Cohort B) OR
 - Participated in Study WA42293 but have discontinued from study treatment (Cohort C; patients who completed treatment in Study WA42293, but no longer wish to take PRM-151 may also join Cohort C)

- For women of childbearing potential: agreement to remain abstinent (refrain from heterosexual intercourse) or use contraception, as defined below:

Women must remain abstinent or use contraceptive methods with a failure rate of <1% per year during the treatment period and for 8 weeks after the final dose of PRM-151.

A woman is considered to be of childbearing potential if she is postmenarchal, has not reached a postmenopausal state (≥ 12 continuous months of amenorrhea with no identified cause other than menopause), and is not permanently infertile due to surgery (i.e., removal of ovaries, fallopian tubes, and/or uterus) or another cause as determined by the investigator (e.g., Müllerian agenesis). The definition of childbearing potential may be adapted for alignment with local guidelines or regulations.

Examples of contraceptive methods with a failure rate of <1% per year include bilateral tubal ligation, male sterilization, hormonal contraceptives that inhibit ovulation, hormone-releasing intrauterine devices, and copper intrauterine devices.

Hormonal contraceptive methods must be supplemented by a barrier method.

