5.1 GENERAL CONSIDERATIONS

All analyses will be reported separated by cohort.

Patients who are rolling-over from Study WA42293 will not be required to repeat safety and efficacy assessment at Day 1 if the visit occurs within 4 weeks of Week 52: in these cases, assessments from Week 52 of Study WA42293 will be used as Day 1 assessments.

The safety analyses will be performed on the safety-evaluable population, unless otherwise specified. Safety will be assessed through descriptive summaries of exposure to zinpentraxin alfa study drug, AEs, and laboratory test results.

All efficacy analyses will be performed on the full analysis set (FAS) population, unless otherwise specified. Patients in Cohort B will be analyzed according to the treatment assigned at randomization by interactive voice/Web-based response system (IxRS) in the parent study.

Cohort B collected data will not be analyzed before unblinding of the code of the treatment received by the patient during the parent Study WA42293. The main analysis will take place at the time of unblinding and main analysis of the parent Study WA42293. If unblinding of the Study WA42293 will occur earlier than the 52-week visit of the last patient enrolled in Cohort B, additional efficacy analysis will be implemented at the time when all patients in Cohort B had their 52-week visit or withdrew from the study, whichever is earlier.

Additional safety update analyses maybe conducted as required by Health Authorities. The final analysis will take place after the last patient last visit (LPLV).

All outputs relevant to Cohort C will have a footnote specifying that most part of the patients has contributed also to Cohort A and Cohort B.

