5.1.1 Treatment/Patient Group Terminology by Cohort

The terminology of treatment/patient groups for each cohort under each analysis population is defined below:

Cohort A

- zinpentraxin alfa: all data for all patients

Cohort B

- Placebo: all data for patients as assigned to placebo during analysis in the parent study (actual or planned, depending on the type of the analysis)

- Zinpentraxin alfa: all data for patients as assigned to zinpentraxin alfa during analysis in the parent study (actual or planned, depending on the type of the analysis)
- All patients

Survival population for Cohort C

- From Cohort A: survival data from patients that discontinued or died from Cohort A
- From Cohort B: survival data from patients that discontinued or died from Cohort B for the following treatments
 - Placebo: survival data for patients as assigned to placebo during analysis in the parent study (planned treatment)
 - Zinpentraxin alfa: survival data for patients as assigned to zinpentraxin alfa during analysis in the parent study (planned treatment)
 - All patients
- Directly from Study WA42293: survival data from patients that have discontinued from study treatment or have completed Study WA42293 and have not wanted to receive open-label zinpentraxin alfa.
 - Placebo: survival data for patients as assigned to placebo during analysis in the parent study (planned treatment)
 - Zinpentraxin alfa: survival data for patients as assigned to zinpentraxin alfa during analysis in the parent study (planned treatment)
 - All patients

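### Survival by parent-study arm is shown only inside groups entered after randomisation, so arm differences may reflect selection, and deaths in the WA42293 year are left out

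*Protocol*

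**What the plan says.** Protocol 3.3.3 commits the sponsor to go on collecting survival after a patient stops, unless consent for this is withdrawn: "For patients who are unable or unwilling to continue with study treatment and/or assessments, the Sponsor will continue to collect their survival data".

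For patients from WA42293, cohort membership is settled after randomisation. One of the alternative routes in Protocol 4.1.1 is "Completed study treatment in Study WA42293 (Cohort B) OR". Cohort C takes those who stopped parent-study treatment, and completers who no longer want the drug.

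SAP 5.1 sets the reporting rule: "All analyses will be reported separated by cohort". SAP 5.1.1 defines placebo and zinpentraxin alfa groups, by parent-study arm, in three places:
- within Cohort B;
- within the Cohort C group from Cohort B: "survival data from patients that discontinued or died from Cohort B for the following treatments";
- within direct Cohort C entrants: "survival data from patients that have discontinued from study treatment or have completed Study WA42293 and have not wanted to receive open-label zinpentraxin alfa".

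SAP 5.4.1 starts time-to-event at OLE Day 1. Its Table 4 censors survival at withdrawal from treatment. SAP Table 2 defines a survival population of everyone who entered, but it is used only for counts (5.2) and as the parent of the Cohort C groups (5.1.1). SAP section 5 says the analysis sections apply to Cohorts A and B. SAP section 2 calls the study non-comparative, with no tests.

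**The concern.** WA42293 randomised patients to drug or placebo, and the extension gives drug to all who continue. A reader shown survival for former placebo and former active patients side by side will read it as early against later start. Within any one of the three groups that reading is not protected by randomisation. To be in the group a patient must have survived WA42293 and then completed, stopped or declined. If patients stopped for different reasons in the two arms, for example deterioration on one and tolerability on the other, the groups differ in prognosis before extension follow-up begins.

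Two further features do not depend on differential stopping. The group of patients who discontinued or died from Cohort B takes in every Cohort B death and leaves out everyone alive on treatment, so its curve is not a survival estimate for any population defined in advance. And every display starts after WA42293, so deaths in the only year in which the arms were assigned different treatment (apart from the extension loading doses) are not counted.

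At stake is a by-arm survival figure that could suggest harm or benefit where there is none, or hide a benefit gained in the parent study.

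**Working it through.** The plan gives no figure to reproduce: no sample size, event count or effect rests on this point. The check is a reading of the text plus illustrations under stated assumptions.

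**1. Route and display**

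| Group | Condition for entry | Time origin | By parent arm? |
|---|---|---|---|
| Cohort B | alive, completed WA42293 treatment, chose to continue | OLE Day 1 | yes |
| Cohort C, from Cohort B | discontinued, or died | not stated for this group | yes |
| Cohort C, direct | alive, stopped or declined | not stated for survival; SAP 5.6.2 gives WA42293 Day 1 for baseline characteristics | yes |
| All randomised in WA42293 | randomisation only | WA42293 Day 1 | not specified |

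**2. Differential stopping, no drug effect.** I simulated 400,000 patients per scenario with a true hazard ratio of 1.00. The documents supply only the median survival of 2 to 5 years (Protocol 3.3.3). Assumed: 1:1 allocation, log-normal frailty with SD 0.8 to 1.0, 15% to 25% stopping in WA42293, 90% roll-over of completers, 15% per year stopping in the extension, and 5 years of extension follow-up. Hazard ratios are former active over former placebo.

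| Stopping in WA42293 | Cohort B | Direct Cohort C | B and direct C pooled | All randomised |
|---|---|---|---|---|
| linked to prognosis on placebo only | 1.04 to 1.11 | 0.72 to 0.88 | 0.99 to 1.01 | 0.99 to 1.01 |
| linked to prognosis equally in both arms | 1.00 to 1.01 | 1.00 to 1.01 | 1.00 to 1.01 | 1.00 to 1.01 |

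A second model (gamma frailty with variance 0.5 to 1.0, initial hazard 0.07 to 0.30 per year, 20% stopping, again linked to frailty on placebo only) gave 2-year cumulative-hazard ratios of 1.09 to 1.19 in Cohort B and 0.54 to 0.70 in Cohort C. Its lowest hazard is below ln 2/5 = 0.14, the value for a 5-year median under constant hazard. The size clearly depends on the model.

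**3. Loss of the WA42293 year, like stopping.** Take gamma frailty with variance 1, so the cumulative hazard is ln(1 + H), where H is the frailty-free cumulative hazard. Assume a hazard ratio of 0.7 in the WA42293 year only, and stopping unrelated to prognosis.
- Hazard 0.14: H at 1 and 3 years is 0.14 and 0.42 on placebo, 0.098 and 0.378 on active.
  - Cohort B, years 1 to 3: ln(1.378/1.098) / ln(1.42/1.14) = 0.227/0.220 = 1.03.
  - All randomised, years 0 to 3: ln(1.378)/ln(1.42) = 0.321/0.351 = 0.91.
- Hazard 0.30: H is 0.30 and 0.90 on placebo, 0.21 and 0.81 on active.
  - Cohort B: ln(1.81/1.21) / ln(1.9/1.3) = 0.403/0.379 = 1.06.
  - All randomised: ln(1.81)/ln(1.9) = 0.593/0.642 = 0.92.

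With stopping linked to prognosis in the same way in both arms, simulation gave 1.01 to 1.05 in Cohort B and 0.90 to 0.93 for all randomised. A real early benefit is absent from the Cohort B display even when stopping is alike.

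**4. The group selected on death.** In the step 2 simulation, 66% to 86% of patients who discontinued or died from Cohort B were dead at 5 years, against 46% to 71% of all Cohort B. Censoring at treatment withdrawal dropped 22% to 30% of Cohort B deaths from the Cohort B curve.

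**5. Limit of the remedy.** In the second model with no drug effect and hazards 0.14 and 0.30, the display proposed below gives 1.03 to 1.05 if half of the surviving stoppers do not join Cohort C, and 1.06 to 1.11 if none join.

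**6. Precision.** If all 600 to 700 patients came from WA42293 (an upper bound, since Cohort A is in that total), deaths after entry are d = n(1 − 2^(−t/m)), with t years of follow-up and median m. The 95% CI factor for a hazard ratio is exp(1.96 × 2/√d). At n = 600, t = 2, m = 5: d = 145, factor 1.38. At n = 700, t = 4, m = 2: d = 525, factor 1.19.

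**The case against.** The strongest reply is scope. Both documents call the study non-comparative, SAP 5.4 rules out testing between the Cohort B groups, and the objective is long-term efficacy, not early against delayed start. That is a sound reason to plan no test. It does not settle how arms displayed side by side will be read. SAP 5.4 asks for 95% CIs wherever possible, the Cohort B slope model has a treatment-by-time term, and SAP 5.6.6 speaks of a treatment effect. The only caution attached to Cohort C is the SAP 5.1 footnote that most of its patients also contributed to Cohorts A and B. That concerns overlap, not selection.

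A reader might infer several stronger things that the documents do not support:
- **That the by-arm displays are biased as a matter of fact.** Between-arm bias with no drug effect needs stopping that differs by arm, and the documents give no stopping rates or reasons by arm. With like stopping it vanishes.
- **That Cohort C exists to complete WA42293 follow-up.** Protocol 3.3.3 does not say so, and Cohort C also receives Cohort A patients from PRM-151-202.
- **That an unbiased comparison is ready from data already held.** Cohort C entry is by invitation (Protocol 3.1.1) and separate consent (8.2), no roll-over rate is given, and Protocol 4.5.3 lists medical history and ongoing adverse events as transferred data, not deaths.
- **That the randomised comparison is made nowhere.** The WA42293 analysis plan is not among these documents.

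**Conclusion.** The point holds as a structural weakness. Every by-arm survival display for WA42293 patients conditions on a post-randomisation event, one conditions on death itself, and all omit the WA42293 year. Neither document specifies an analysis of Cohorts B and C together by randomised arm.

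The between-arm bias is a risk whose size and direction cannot be derived from the documents. The illustrations put it at a few percent to about 20% in Cohort B, and at a 12% to 46% lower apparent hazard for former active patients in Cohort C, when stopping is linked to prognosis on placebo only. Reversing that assumption would reverse the direction. The distortion from grouping on discontinuation or death, as an absolute survival estimate, and the omission of the WA42293 year follow from the definitions and need no such assumption. No safety or primary conclusion depends on this; it affects how survival, a listed efficacy endpoint, can be interpreted.

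**What to change.** In SAP 5.1.1 and 5.4.1:

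1. Add one descriptive all-cause survival display of all patients randomised in WA42293, by randomised arm, from WA42293 Day 1. Join parent-study deaths with Cohort B and Cohort C follow-up, regardless of treatment status. No test is needed.
2. Give Kaplan-Meier probabilities at fixed times with 95% CIs, and the number per arm who never entered WA42294. Censor those patients at last WA42293 contact, or at registry status where available (Protocol 4.6.2 and 5.3.4 already foresee registries after withdrawal or loss to follow-up).
3. Describe it as a contrast of assigned policies, since placebo patients who go directly to Cohort C never start the drug.
4. Replace the by-arm display of patients who discontinued or died from Cohort B, or label it and the other within-cohort arm displays as non-randomised. If nothing else is done, the label alone would help.

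The cost is SAP text, one figure and table, and a linked dataset, because parent-study survival has to be brought in. No visit or treatment changes. The display is less biased, not unbiased: patients who never enter WA42294 are censored, and bias remains if non-entry differs by arm. The interval will also be too wide to settle a modest difference.

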3.3.4 Rationale for Biomarker Assessments

Exploratory biomarker samples will be collected from Cohort A and B during the study and may be used to assess PRM-151 pharmacodynamics and the relationship between IPF-related biomarkers, disease progression, and clinical status.

4. MATERIALS AND METHODS

4.1 PATIENTS

4.1.1 Inclusion Criteria

Approximately 600–700 patients with IPF will be enrolled in this study.

Patients must meet the following criteria for study entry:

- Signed Informed Consent Form
- In the opinion of the Principle Investigator, participation in the study is in the best interest of the patient

- Ability to comply with the requirements of the study protocol, according to the investigator's best judgment
- Taken part in a previous study of PRM-151, as follows:
 - Participated in Study PRM-151-202 (completed the 28-week placebo-controlled period and entered the OLE), and tolerated the study drug in the opinion of the investigator (Cohort A) OR
 - Completed study treatment in Study WA42293 (Cohort B) OR
 - Participated in Study WA42293 but have discontinued from study treatment (Cohort C; patients who completed treatment in Study WA42293, but no longer wish to take PRM-151 may also join Cohort C)

- For women of childbearing potential: agreement to remain abstinent (refrain from heterosexual intercourse) or use contraception, as defined below:

Women must remain abstinent or use contraceptive methods with a failure rate of <1% per year during the treatment period and for 8 weeks after the final dose of PRM-151.

A woman is considered to be of childbearing potential if she is postmenarchal, has not reached a postmenopausal state (≥ 12 continuous months of amenorrhea with no identified cause other than menopause), and is not permanently infertile due to surgery (i.e., removal of ovaries, fallopian tubes, and/or uterus) or another cause as determined by the investigator (e.g., Müllerian agenesis). The definition of childbearing potential may be adapted for alignment with local guidelines or regulations.

Examples of contraceptive methods with a failure rate of <1% per year include bilateral tubal ligation, male sterilization, hormonal contraceptives that inhibit ovulation, hormone-releasing intrauterine devices, and copper intrauterine devices.

Hormonal contraceptive methods must be supplemented by a barrier method.

The reliability of sexual abstinence should be evaluated in relation to the duration of the clinical trial and the preferred and usual lifestyle of the patient. Periodic abstinence (e.g., calendar, ovulation, symptothermal, or postovulation methods) and withdrawal are not adequate methods of contraception. If required per local guidelines or regulations, locally recognized adequate methods of contraception and information about the reliability of abstinence will be described in the local Informed Consent Form.

- For men: agreement to remain abstinent (refrain from heterosexual intercourse) or use a condom, and agreement to refrain from donating sperm, as defined below:

With a female partner of childbearing potential or pregnant female partner, men must remain abstinent or use a condom during the treatment period and for 8 weeks after the final dose of PRM-151 to avoid exposing the embryo. Men must refrain from donating sperm during this same period.

The reliability of sexual abstinence should be evaluated in relation to the duration of the clinical trial and the preferred and usual lifestyle of the patient. Periodic

abstinence (e.g., calendar, ovulation, symptothermal, or postovulation methods) and withdrawal are not adequate methods of preventing drug exposure. If required per local guidelines or regulations, information about the reliability of abstinence will be described in the local Informed Consent Form.

4.1.2 Exclusion Criteria

Patients who meet any of the following criteria will be excluded from study entry:

- Received any experimental treatment other than PRM-151 within 4 weeks or five half-lives of the experimental drug, whichever is longer, prior to the first dose in the OLE study.
- Receiving strong inhibitor or inducer of CYP1A2 in patients taking pirfenidone
- Receiving potent inhibitor or inducer of P-gp in patients taking nintedanib.
- Acute respiratory or systemic bacterial, viral, or fungal infection at the first visit of the OLE, or within 2 weeks of the first visit for patients joining Cohort A (from Study PRM-151-202).
- History of smoking (including cigarette, cannabis, cigar, pipe, and vaping) within 3 months prior to the first visit in the OLE.
- History of alcohol or substance use disorder within 2 years prior to the first visit of the OLE or known or suspected active alcohol or substance-use disorder.
- History of severe allergic reaction or anaphylactic reaction to PRM-151.
- Clinically significant abnormality on ECG during eligibility assessment that, in the opinion of the investigator, may pose an additional risk in administering study drug to the patient
- Prolonged corrected QT interval >450 ms (for men) or >470 ms (for women) based on the Fridericia correction formula.
- Clinically significant laboratory test abnormalities (hematology, serum chemistry, and urinalysis) that, in the opinion of the investigator, may pose an additional risk in administering study drug to the patient.
- Any of the following laboratory abnormalities known at the time of the first visit
 - ALT and/or AST $\geq 2.5 \times$ upper limit of normal (ULN)
 - Total bilirubin $\geq 2 \times$ ULN
- Pregnant or breastfeeding, or intending to become pregnant during the study (for Cohort A or B patients).

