4.6 TREATMENT, PATIENT, STUDY, AND SITE DISCONTINUATION

4.6.1 Study Treatment Discontinuation

Patients must permanently discontinue study treatment if they experience any of the following:

- Any medical condition that the investigator or Sponsor determines may jeopardize the patient's safety if he or she continues to receive study treatment
- Investigator or Sponsor determination that treatment discontinuation is in the best interest of the patient
- Pregnancy
- Anaphylaxis or serious hypersensitivity reaction
- Grade 4 IRR or two Grade 3 IRRs (the first occurrence of the Grade 3 IRR can be either in the Phase II Study PRM-151-202, Phase III Study WA42293, or in this Study WA42294)
- Lung Transplant

The primary reason for study treatment discontinuation should be documented on the appropriate eCRF. Patients who discontinue study treatment prematurely will not be replaced.

If a patient discontinues study drug treatment prematurely for any reason, patients will return to the clinic for a treatment discontinuation visit 4 weeks after the final dose of study drug (see [Appendix 1](#) for additional details). Every effort should be made to collect

safety data at time of the treatment discontinuation visit. Survival data will continue to be collected unless the patient declines to be included in Cohort C.

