9.2 PROTOCOL DEVIATIONS

The investigator should document and explain any protocol deviations. The investigator should promptly report any deviations that might have an impact on patient safety and data integrity to the Sponsor and to the IRB/EC in accordance with established IRB/EC policies and procedures. The Sponsor will review all protocol deviations and assess whether any represent a serious breach of Good Clinical Practice guidelines and require reporting to health authorities. As per the Sponsor's standard operating procedures, prospective requests to deviate from the protocol, including requests to waive protocol eligibility criteria, are not allowed.

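### Read literally, eight exclusion criteria not limited by cohort, including anaphylaxis to PRM-151, also bar direct entry from WA42293 into the untreated survival Cohort C

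*Protocol*

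**What the plan says.** - **Scope of the list.** Protocol 4.1.2 begins "Patients who meet any of the following criteria will be excluded from study entry". The synopsis uses the same lead-in. Neither names a cohort.
- **Cohort C is an entry route.** Protocol 4.1.1 lists three routes into the study. The third is "Participated in Study WA42293 but have discontinued from study treatment", which leads to Cohort C. Patients who completed WA42293 treatment but want no more drug may also use it.
- **Criteria without a cohort limit.** Examples are "History of severe allergic reaction or anaphylactic reaction to PRM-151", "Prolonged corrected QT interval >450 ms (for men) or >470 ms (for women) based on the Fridericia correction formula" and "Receiving strong inhibitor or inducer of CYP1A2 in patients taking pirfenidone".
- **The one criterion with a full cohort limit.** It reads "Pregnant or breastfeeding, or intending to become pregnant during the study (for Cohort A or B patients".
- **No discretion at the site.** Protocol 4.5.1 asks for every eligibility criterion to be confirmed before enrollment, and 9.2 says that "requests to waive protocol eligibility criteria, are not allowed".
- **What Cohort C is for.** Protocol 3.1.1 gives it no treatment and no safety or efficacy assessments. Protocol 3.3.3 says that survival will still be collected for patients who cannot or will not go on with treatment.
- **The same event inside this study.** Protocol 4.6.1 lists "Anaphylaxis or serious hypersensitivity reaction" as a reason to stop treatment permanently. Under 3.1.1 and 8.2 the patient then passes into Cohort C automatically.
- **How the data are used.** SAP section 4 (Table 2) defines the survival population as everyone who entered the study. SAP 5.1.1 reports Cohort C patients who came directly from WA42293 as a separate group, split by parent-study arm.

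**The concern.** Several of these exclusions concern the safety of dosing, and Cohort C patients are not dosed, so there the exclusions protect nobody. Applied literally, they turn away some of the patients whom the cohort was set up to follow. The clearest case is a patient who stopped WA42293 treatment because of anaphylaxis to PRM-151. That patient meets the Cohort C inclusion criterion and an exclusion criterion at the same time.

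What is at stake is who stands in the direct-from-WA42293 survival summary. Patients turned away never enter, so they are missing from the survival population. The death-registry provisions in 4.6.2 and 5.3.4 do not recover them, because those cover patients who withdraw or are lost after entry. The reaction criterion also depends on exposure to PRM-151, so its effect need not be equal in the two parent arms.

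**Working it through.** No figure in the plan bears on this, and no sample size calculation was made (Protocol 6.1, SAP 3). The check is a reading of the criteria side by side.

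**Step 1: sort the 12 top-level criteria in Protocol 4.1.2.**

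- Limited to Cohorts A and B (1): pregnancy or breastfeeding.
- Tied to dosing by their own wording (3): experimental treatment, timed back from the first OLE dose; ECG abnormality and laboratory abnormality, each judged by the added risk of giving study drug. An undosed patient cannot meet these.
- Neither (8): CYP1A2 interaction, P-gp interaction, infection, smoking, alcohol or substance use, severe allergic or anaphylactic reaction to PRM-151, QTc, and ALT/AST/bilirubin. The infection item names Cohort A, but only for its two-week look-back.

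Count: 1 + 3 + 8 = 12. As written, eight reach Cohort C.

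**Step 2: can a limit to Cohorts A and B be read in?** The protocol states such a limit where it is meant: in the pregnancy criterion, and in 4.4.2 for prohibited therapy. Protocol 5.3.4 adds that women who became pregnant in WA42293 may join Cohort C. No section does the same for any of the eight. Stating the limit for one item makes it hard to imply it for the rest.

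**Step 3: follow one event along two paths.**

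- Anaphylaxis to PRM-151 in Cohort A or B: treatment stops (4.6.1), the patient moves to Cohort C without a new eligibility check (8.2), and survival is followed.
- Anaphylaxis to PRM-151 in WA42293: treatment stops, 4.1.1 admits the patient to Cohort C, 4.1.2 excludes the same patient, 9.2 rules out a waiver, and survival is not followed here.

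**Step 4: trace this into the analysis.** The survival population holds only those who entered (SAP Table 2). Direct entrants are shown by parent arm (SAP 5.1.1). A true reaction to PRM-151 requires PRM-151, so within WA42293 it can arise only in the active arm. The criterion can therefore remove active-arm patients and leave placebo patients in. While the parent blind holds (Protocol 4.2.1), sites cannot tell which drug a reaction was to and cannot apply the criterion reliably. Some placebo patients might be turned away by mistake. The selection by arm is thus a possibility that the rule creates, not a certainty.

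**Step 5: check what lies outside its reach.** The efficacy survival endpoint uses the full analysis set of Cohorts A and B (SAP 5.4) and censors at withdrawal from treatment (SAP 5.4.1, Table 4). Direct Cohort C entrants are not in it.

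**The case against.** The best answer is that this is a drafting oversight and that the intent is plain. Protocol 3.1.1 invites patients who stopped or completed WA42293 into Cohort C, and 3.3.3 includes those unable to continue. The inclusion/exclusion check and the ECG and laboratory rows appear only in Appendix 1, for Cohorts A and B; Appendix 2 asks Cohort C for survival status alone. Several of the eight criteria also have little practical reach. Infection, smoking, liver tests and the alcohol/substance look-back are anchored to a first visit that a remotely followed cohort does not clearly have. No ECG is scheduled to reveal QTc. The CYP1A2 and P-gp items apply only to patients on pirfenidone or nintedanib. No tests are planned, and SAP 5.1 expects most Cohort C patients to have come through Cohorts A and B.

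Most of this stands, and it limits the consequence. It does not remove the conflict. Appendix 2 also leaves out consent, which 8.2 requires for direct entrants, so its silence on eligibility proves little. Sites that follow the text and sites that follow the intent will enroll different patients.

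Three stronger readings are tempting, and the documents do not support them:

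- A reader might infer that every criterion except pregnancy applies to Cohort C. Three others limit themselves to dosing.
- A reader might infer that anyone who stopped WA42293 for a severe allergic reaction is barred. The criterion is a reaction to PRM-151, which a placebo patient cannot truly have had.
- A reader might infer selection against worsening IPF. The list has no FVC, DLCO, oxygen, exacerbation or transplant criterion, so progression alone excludes nobody.

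**Conclusion.** The point holds as a conflict within the protocol. Read literally, eight exclusion criteria bar direct entry from WA42293 into an untreated survival cohort, contrary to 3.1.1, 3.3.3 and 4.1.1 and to the handling of the same reaction in Cohorts A and B. One of the eight can act on a single parent arm.

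The size cannot be computed, because the documents do not say how many WA42293 patients meet a criterion or how their mortality differs. Even the direction of any shift in survival is unknown. For the reaction criterion the documents suggest rarity: one anaphylactic reaction is reported across Phase I/II, in a myelofibrosis patient (Protocol 5.1.2), and all infusion-related reactions in PRM-151-202 were Grade 1 or 2 except one Grade 3 (5.1.1).

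A reader might try to put a number on it. Let a fraction q of potential entrants be barred, with HR times the hazard h of the rest. Two-year survival is then overstated by q × [exp(−2h) − exp(−2h × HR)]. The median survival of 2 to 5 years in 3.3.3 gives h = ln 2 / 2 = 0.347 to ln 2 / 5 = 0.139 per year.

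- q = 5%, HR = 1.5, h = 0.139: 0.05 × (0.758 − 0.660) = 0.5 points.
- q = 15%, HR = 3, h = 0.347: 0.15 × (0.500 − 0.125) = 5.6 points.

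That range should not be cited as the effect. Both q and HR are invented, and nothing in the documents links these criteria to higher mortality. The effect is probably small. It is confined to a descriptive summary and leaves the Cohort A and B survival endpoint untouched. The correction is still worth making, because the selection comes from a rule and is easily removed.

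**What to change.** State in Protocol 4.1.2 and in the synopsis that the exclusion criteria apply to Cohorts A and B only, as is already done for pregnancy and, in 4.4.2, for prohibited therapy. Leave the general inclusion criteria in force for Cohort C: consent, the investigator's best-interest judgment, ability to comply, and prior participation in WA42293. Nothing here calls for dropping those.

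The cost is one line in two places of the next amendment. It adds no procedure and no drug exposure, since Cohort C patients are not dosed. If sites have already applied the present text, a count by parent arm of patients turned away from Cohort C would show whether it mattered.
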